### **(e) Procedures**

#### **Overview of Procedures**

Summary of data collection: Aim 1 will consist of three phases. In Aim 1 Phase 1, we will conduct individual in-depth interviews (IDIs) with pregnant ALHIV and dyadic interviews (DI) with pairs of pregnant ALHIV and their family member caregiver. In Aim 1 Phase 2 we will conduct focus group discussions (FGDs) with pregnant ALHIV. In Aim 1 Phase 3 we will carry out a pilot study with pregnant ALHIV serving as prototype testers and will collect survey data (baseline and two-weeks post-intervention) and qualitative data (participant thoughts and field staff notes). In Aim 2, we will conduct two rounds of FGDs with family member caregivers of an ALHIV.

#### **What Participants Will Do**

Individual in-depth interviews (IDIs) of adolescents (Aim 1 Phase 1, Component 1): All IDIs will be conducted by trained, experienced interviewers able to speak fluently in the local languages (Luo, Swahili, and English). The research team will develop a semi-structured interview guide. Questions asked of the pregnant ALHIV will include ones pertaining to their experiences disclosing their HIV and/or pregnancy status to caregiving family members, receiving support from caregivers, with stigma due to their HIV and/or pregnancy status, and perspectives about SMS and digital intervention features, images, and preferences. IDIs will be conducted at venues that offer privacy and are quiet, convenient, and comfortable for participants. Each interview will take about 60-90 minutes.

Dyadic Interviews with adolescents and caregivers (Aim 1 Phase 1, Component 1): Research staff will use the same procedures for conducting the Dis as described above for the IDIs (i.e., semi-structured interview guide, private and convenient venues for the interviews, 90-minute sessions). However, in these interviews, the adolescent and their caregiver will be interviewed together. Research staff will ask

them about their disclosure experiences, what could have improved the experience, the best ways to involve caregivers, and advice they have for people in a similar circumstance.

The research team will use the IDI and DI findings, led by our 3C Institute collaborators, to develop initial specifications and mock-ups of the digital intervention.

**FGDs with adolescents (Aim 1 Phase 2, Component 2) and caregivers (Aim 2, Component 4):** For Aim 1 there will be 4 FGDs (8 participants each) conducted with pregnant ALHIV (2 rural and 2 urban). For Aim 2, there will be 4 FGDs (8 participants each) conducted with caregiving family members (2 rural and 2 urban) in Round 1 and 4 FGDs in Round 2 (2 rural, 2 urban). FGD sessions will be facilitated by a trained KEMRI moderator fluent in the local languages who will use a semi-structured guide. Each session will last up to two hours. The adolescents will be asked for feedback on the content and flow of the intervention module and their opinion on the mock-ups (e.g., appropriateness, realism, appeal, and plans for using text messaging). Caregivers in Round 1 will be asked about our plans for developing a digital intervention for ALHIV and approaches for involving family caregivers. Caregivers in Round 2 will be asked for feedback about the final Aim 1 intervention prototype and views on a potential complementary digital intervention for caregivers. All FGDs will be conducted in a location providing privacy and confidentiality.

Using Aim 1 findings, the research team will develop an intervention prototype. As part of this process, PIRE and KEMRI staff will test versions in order to finalize the prototype.

**Pilot study with adolescents (Aim 1, Component 3):** The pregnant ALHIV participants will complete a 40-50-minutes baseline survey that includes questions about demographics, HIV and pregnancy stigmas, and disclosure. All participants will receive a one-on-one intervention session in which they will be provided with a study mobile phone with internet access, guided on how to access the prototype intervention, and instructed to go through the intervention. Research staff will take notes of observations made while participants are using the app. Immediately after participating in the intervention, the adolescents will complete a questionnaire asking about the intervention's acceptability and usability. Intervention sessions may last up to two hours. Altogether, the baseline data collection and intervention session will last approximately 3 hours. Participants will take a follow-up survey two weeks after the intervention session, which will last about 40-50 minutes.

**All participants (Aims 1 and 2, Components 1 through 4):** The study will collect private identifiable information from all participants. Socio-demographic data (e.g., age, gender, educational attainment) and written consent forms (containing participant names) will be collected from all participants. Participants in the interviews and pilot study will be asked questions about their own lives and experiences.

**COVID-19 Prevention Protocols (all participants):** [name] (KEMRI co-investigator) is overseeing operations of a research project monitoring HIV infections among pregnant women in Siaya County. We will follow his study's protocols (adapted as needed), which are compliant with Kenya's Ministry of Health guidelines for COVID-19 prevention. Study staff and research participants will be screened for COVID-19 symptoms before engaging in study procedures (taking temperature, screening for symptoms, and compulsory handwashing/sanitizing). Staff or participants who screen positive will be directed to appropriate testing and health care resources. Study staff will receive training on COVID-19 mitigation measures. Staff and participants will be required to wear face masks during all face-to-face interactions,

follow hand hygiene protocols, and adhere to physical distancing rules. Staff will sanitize data collection tools. Data collection activities will be conducted in open outdoor spaces whenever feasible and when privacy can be ensured. When that is not possible, the activities will be conducted indoors with adequate ventilation.

## **11. DATA MANAGEMENT:**

**Data Collection and Management:** Data sources will include electronic data files, audio-recordings, transcripts, and field notes obtained from research activities which will include interviews, focus groups, and surveys. Research team members will audio-record the interviews and focus groups and take notes. All audio recordings will be transcribed and translated. The research team will develop and use codebooks for each qualitative research activity to analyze the data. For the pilot study, the research team will analyze the pre- and post-treatment questionnaire data to assess if the intervention produced clinically meaningful improvements on outcomes of interest. Participants will complete a survey at baseline, immediate post-intervention, and two-week follow-up. We will use an adaptation of the user version Mobile Application Rating Scale (uMARS), modified for our study, to assess the intervention's acceptability and usability. Other measures, based on our conceptual framework (Fig. 1), will include demographics, stigma (HIV: anticipated from family members, internalized, coping; pregnancy: internalized), disclosure self-efficacy, and disclosure to family members. Survey data will be collected using computer-assisted interviewing (CAI) techniques on secure password-protected devices. All study data will be transferred from data collection devices to KEMRI's secure servers daily. Data will be transferred from KEMRI to PIRE as encrypted data files. At PIRE, the data will be stored on secure servers. Only research staff authorized by the PI ([name]) and Co-PI ([name]) will have access to the data. PIRE staff will conduct further data cleaning, coding, and data analysis.

## **12. ETHICAL CONSIDERATIONS**

### **(a) Human Subjects**

Informed Consent: All study participation will be voluntary. Informed consent will be obtained from participants by trained research staff at each stage of the recruitment and enrollment process. Information provided as part of the consent process will include the purpose of the research, study procedures, explanation of possible risks and safeguards, and explanation that participation is voluntary.

Potential participants who are identified by MCH providers will be offered options about how to connect the individual with study staff (giving verbal consent for providers to share the person's contact information with study staff, receiving contact information of study staff, or allowing the provider to call study staff to schedule a meeting). Research staff will contact potential participants to introduce themselves and provide information. Individuals who are still interested in participating will be invited to meet in private where screening and consent procedures will be administered. Following a script, research staff will obtain verbal consent from individuals prior to screening them for study eligibility. Study staff then will obtain written informed consent from each eligible individual before the person participates in any research activity. Staff will administer an assessment of adequate understanding of the consent information, which we have done in previous research. For additional protection of participants in this study, all research staff will receive training on protection of human subjects including on confidentiality, the ethical conduct of informed consent procedures, administering the assessment of consent comprehension, and reviewing assessment answers and consent form information with the adolescent. Moreover, research staff will be experienced in conducting HIV-related studies with vulnerable youth, and skilled in counseling vulnerable youth, identifying distressed youth,

and interacting with the caregivers of vulnerable youth. They will also be knowledgeable about the study sites, cultural nuances, and fluent in local languages.

**Request for waiver of parental consent and justification:** We are requesting a waiver of parental consent to protect the confidentiality of adolescent participants, including those who are 15-17 years old, who will not have disclosed their HIV and/or pregnancy to their parents. Involving parents of those who have not disclosed their HIV and/or pregnancy status in the consenting process would result in a breach of confidentiality. Pregnant unmarried ALHIV is an understudied, underserved, and hard-to-reach population. Studies are urgently needed to better understand their lived experiences, the barriers they face in, and factors that facilitate, disclosure and uptake of services. The goal of our study is to examine these issues and to develop an approach to enhance disclosure to caregivers and thereby uptake of critical health services. Our study procedures balance the need to inform caregivers about the study without breaching the confidentiality of adolescent study participants.

We are requesting IRB approval to allow youths 15-17 years old to give consent for themselves and to not obtain parent/guardian consent for those youths. In Kenya minor adolescents are considered emancipated minors if they are pregnant, heading a household or are parents and are thus treated as adults [See National AIDS and STI Control Programme (NASCOP) and Kenya Medical Research Institute (KEMRI) (2015). Guidelines for Conducting Adolescents Sexual and Reproductive Health Research in Kenya. <http://icop.or.ke/wp-content/uploads/2016/10/Adolescents-Guidance-on-HIV-SRH-Research.pdf>.] However, as a culturally appropriate courtesy to the families in Kenya, and only with permission from the adolescent participant, we will inform parents, guardians, and/or household heads about the study and the 15-17-year-old adolescent's participation. While doing so, research staff will describe the study in a very general way that will not reveal undisclosed information about the adolescent. Research staff will be trained to ask all participants if they would like the staff to provide this information to their parent. The staff will be available to answer any questions from the adolescents and parents, and they will be trained to give the adolescent and parent time to consult with each other alone if the adolescent seems to want that. In addition, as stated in the consent form, at any time, a participant may change their mind and withdraw from the study. We have successfully used similar procedures in previous studies.

**Request for waiver of documentation of informed consent:** We plan to obtain verbal consent without written documentation for participants to be asked screening questions to determine their eligibility to participate in the study. The reason is that the only record linking the subject and the research would be the consent document the main risk for that person would be a risk of confidentiality.

**Risk of inadvertent disclosure of HIV and/or pregnancy status:** The young woman's HIV status or pregnancy could be inadvertently revealed to family or community members and result in her experiencing stigma. This could happen if someone who does not already know about the adolescent's pregnancy and/or HIV status were to learn that the adolescent or a caregiver is participating in a study for pregnant ALHIV and their caregivers. Accidental disclosure also could occur if a bystander were to overhear an interview or other data collection session in which HIV and/or pregnancy status is revealed. Although participants in the FGDs and pilot study interviews will not be asked personal questions, it is possible that some participants could reveal their HIV and pregnancy status when answering questions. A potential consequence of inadvertent HIV or pregnancy disclosure is violence from a partner, family member, or other person who is upset or who blames the young woman. In addition, adolescent or

caregiver participants could worry about such accidental disclosure occurring, which could result in them experiencing stress and anxiety.

**Risk of emotional distress during data collection sessions:** Some of the adolescent and caregiver participants in the interviews or pilot study could feel uncomfortable or emotionally distressed answering questions about themselves or their family member being pregnant; being HIV-infected; or experiencing problems regarding stigma, disclosure or social support. It also is possible that some participants may think about and disclose upsetting events (e.g., sexual abuse, intimate partner violence, or interpersonal conflict) during the data collection session. FGD participants will not be asked personal questions, but some individuals could potentially think about personal and sensitive thoughts during the research activity.

**Safeguards for inadvertent disclosure of HIV or pregnancy status:** Interview, FGD, and pilot study sessions will be conducted at venues that offer privacy and confidentiality. IDIs and pilot study sessions will be conducted individually. Research staff will be sensitive to participants having various disclosure circumstances and to the potential risks of accidental disclosure. We will use our experience from previous studies when entering homes and communicating with household members to ensure our participants' safety and confidentiality. Only caregivers who know both conditions (HIV-positive status and pregnancy status) of the adolescent they are caring for will be recruited to participate in the dyadic interviews. We will follow procedures to protect data security (described below). We have not come across in any of our previous studies situations in which an adolescent became exposed to violence due to participating in our study. However, we will employ research field staff who are either trained as nurses or counselors or experienced in data collection; will be from the local region and knowledgeable about cultural nuances; and will have experience with HIV studies and working in rural and low-income settings. Like prior studies, staff will receive further training for this study, will have a list of resources to help participants in need, and will be prepared to address potential adverse situations.

**Safeguards for emotional distress during data collection sessions:** Participants may choose to not answer particular questions and to stop their study participation at any time. Field staff will be trained to offer referrals, based on available services within the community, if a young woman were to disclose she has been a victim of sexual abuse, violence or other traumatic experience. Staff will be trained to discuss sensitively the young woman's disclosed experience. Field staff also will be trained to monitor for emotional upset or anxiety during or as a result of the data collection session among any of the participants and to offer support and referrals for services, if they are available. In collaboration with our KEMRI partners, we developed a list of available resources and services for referral purposes in our previous study for adolescent participants in need of psychological, social and medical services. We will update the list and require research staff to distribute a copy to **all** study participants at the conclusion of data collection activities. For adolescents who are identified as distressed, express a need for services, or have not disclosed their pregnancy and/or HIV status to a caregiver, research staff will provide active referrals to services in the community, e.g., antenatal care (ANC), prevention of mother-to-child HIV transmission (PMTCT), HIV treatment and care, counseling, and support with facilitated disclosure.

**Data security:** Unique ID codes will be attached to data (including transcripts and audio-recording files) instead of participant names or other personal identifiers. Data, any lists of names and ID codes, and consent forms will be stored in locked cabinets (if paper) or password-protected (if electronic). No

reports will link individuals' names with data; study results will be reported as aggregate data. Research staff will have access to data only on a need-to-know basis.

Study monitoring and oversight: The PI will obtain approval for the study from the PIRE and KEMRI IRBs. Research staff will receive training in protection of human subjects, research protocols, use of the study's Data Safety and Monitoring Plan (DSMP), and maintaining participant confidentiality. Input will be obtained from the Kenyan team to ensure our plans for monitoring participant safety are appropriate to the local situation, and staff will be trained on the procedures. The PI, co-investigators, and study staff are experienced in conducting research in sub-Saharan Africa, including in the Nyanza region in Kenya and in data collection with HIV-infected adolescents, pregnant adolescents, and family member caregivers. The PI is experienced in monitoring participant safety of HIV-infected, pregnant, and emotionally distressed youth and overseeing field work in Kenya. The study will receive review and oversight from the IRBs. Details of our DSMP are provided in an attachment.

Benefits: Participants may experience personal satisfaction from communicating with researchers about topics relevant to pregnant ALHIV such as stigma, disclosure and family support; being treated as knowledgeable stakeholders; and being part of a study that could potentially help people in similar circumstances of need. The adolescents who participate in the pilot study may benefit from receiving the digital intervention session which will be designed to help adolescents like them improve stigma knowledge and coping skills, HIV and pregnancy disclosure skills, and enlisting support of caregiving family members. The study's risks are reasonable in relation to the potential benefits to participants and others.

(b) **Animal Subjects.** Not applicable.

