all conducted in the Nyanza region. Co-Investigators (Co-Is) include **[name]**, who led the qualitative component of [name] supplement. He also co-led a study in the U.S. to examine experiences among patients diagnosed during acute HIV infection and the ethical issues to consider when involving this population in clinical research (R21AI120549). **[name]** is based at KEMRI and was a Co-I on the ethics parent R01 and supplement. He has extensive knowledge about the local Kenyan health system and has led several HIV prevention/control, care, and treatment programs as a clinician and program manager. Currently, he leads a Gates Foundation funded ANC surveillance project in one sub-county within Siaya County. There are 1,263 pregnant adolescents aged 15-19 in this project. Of these, 63 (5%) are HIV-infected; half (32/63) are single. **[name]** is Chief Executive Officer at 3C Institute. She has extensive experience with development and implementation of both universal and targeted positive behavioral interventions for adolescents. Her recent research focused on developing and implementing evidence-based interventions via emergent technology and intelligent tutoring systems. She has served as PI and co-PI on several NIH-funded projects to develop culturally specific digital interventions. See Appendices B1-B3 for additional information about Drs. [name], [name], and [name], including publications.

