**Aim 1 adolescent participants:** N=24 adolescents will participate in an IDI and N=24 adolescents will participate in a dyadic interview with a family caregiver (**Component 1**), N=32 adolescents will participate in an FGD (4 FGDs comprised of 8 participants each, **Component 2**), and N=30 adolescents will participate in the pilot study (**Component 3**). Inclusion criteria: All adolescent participants will be female, currently pregnant, unmarried, 15-19 years old and have been diagnosed with HIV and aware of this diagnosis. They will collectively have a range of disclosure experiences (disclosed pregnancy and HIV status to a caregiving family member, disclosed one of the two conditions, has not disclosed either condition). Exclusion criteria: An adolescent will be excluded if she: (1) does not meet all inclusion criteria, (2) already participated in a study activity, or (3) does not show understanding of consent based on our consent assessment.

**Aim 1 caregiving family member participants (N = 24, Component 1):** They will be the family member who participates in the dyadic interview with an ALHIV. Inclusion criteria: Caregiving family member (e.g., parent, guardian, grandparent, sibling or other relative) of a pregnant unmarried ALHIV who is aged 15-19. They will be age 20 or older and may be female or male. Exclusion criteria: Caregivers will be excluded if they: (1) do not meet all inclusion criteria, (2) already participated in a study activity, or (3) are a romantic/sexual partner or a family member of a romantic/sexual partner of a pregnant ALHIV (rather than a member of her family).

**Aim 2 caregiving family member participants (N = 64, Component 4):** Inclusion criteria: Like the Aim 1 caregivers, they will be a caregiving family member of a pregnant unmarried ALHIV who is aged 15-19, aged 20 or older, and may be female or male. They may or may not be the family member of an Aim 1 participant. They will participate in one FGD session. Exclusion criteria: Caregivers will be excluded if they: (1) do not meet all inclusion criteria, (2) already participated in a study activity, or (3) are a romantic/sexual partner or a family member of a romantic/sexual partner of a pregnant ALHIV (rather than a member of her family).

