**(Components 1, 2, and 3):** For individual in-depth interviews (IDIs) and focus group discussions (FGDs), we will select adolescents who have disclosed and not disclosed their pregnancy and/or HIV status to a caregiver. For dyadic interviews (DIs), we will purposively select adolescents who have disclosed both conditions to their caregiver. Pilot study participants will not have disclosed at least one of the two conditions to a caregiver. In both our urban and rural sites, we will recruit participants from maternal and child health (MCH) clinics in public health facilities. Kisumu and Siaya County Directors of Health will assist us to identify public health facilities serving large numbers of pregnant ALHIV. As in our previous research, we will visit the facilities to seek assistance from MCH providers in referring potential participants to our study staff. To protect their privacy, MCH staff will inform potential participants (i.e., pregnant unmarried ALHIV aged 15-19) about our study and ask if they are interested in participating.

MCH providers will give interested individuals the following options: (1) give verbal consent to the MCH provider to allow their contact information to be shared securely with study staff, (2) be given contact information of the study staff so that the adolescent can call at her convenience, and/or (3) give verbal consent for the MCH provider to call study staff in their presence to schedule a meeting. Providers assisting with recruitment will be trained in human subjects protections and given a script to use when informing potential participants about the study. We will adjust our recruitment procedures based on any new clinic/hospital protocols that have been implemented to mitigate the spread of COVID-19. Providers will receive financial support to assist with recruitment (e.g., for cell phone airtime and transport).

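### Attending an adolescent focus group itself tells the other members that a girl is pregnant and living with HIV; the risk text and safeguards do not address this route

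*Combined protocol and SAP*

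**What the plan says.** Section 10(c), Study populations, sets one eligibility rule for all adolescents: "All adolescent participants will be female, currently pregnant, unmarried, 15-19 years old and have been diagnosed with HIV and aware of this diagnosis". For Component 2 it plans that "N=32 adolescents will participate in an FGD (4 FGDs comprised of 8 participants each".

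Section 10(d), Sampling procedure, states that for individual interviews and "focus group discussions (FGDs), we will select adolescents who have disclosed and not disclosed their pregnancy and/or HIV status to a caregiver". Recruitment runs through maternal and child health clinics and through flyers that participants hand on in their own communities.

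Section 12(a) deals with inadvertent disclosure in two steps. It first says, for the study as a whole, that a girl's status could come out if a person who did not know it found out that she was taking part. It then turns to focus groups and pilot interviews, says that no personal questions will be asked there, and adds that "it is possible that some participants could reveal their HIV and pregnancy status when answering questions". Violence is listed as a potential consequence of inadvertent disclosure.

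The safeguards that follow are private venues, staff sensitivity and training, care when entering homes, a rule on what caregivers in dyadic interviews must already know, and data security. On session format, the text says that "IDIs and pilot study sessions will be conducted individually". Girls who have not disclosed to a caregiver are offered active referral to services.

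**The concern.** The sentence on focus groups makes disclosure depend on what a girl says. In a group where every member must have both conditions, it depends on her being there. Withholding personal questions cannot prevent that.

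The gap is internal to the protocol, which elsewhere treats participation as sensitive information. Section 10(d) does not ask girls with an undisclosed condition to nominate a caregiver, for safety reasons. Section 12(a) has staff describe the study to parents only in general terms. The adolescent focus group is the setting where other people are sure to see that a girl is taking part, and the same reasoning is not applied there.

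Two things are at stake. One is the accuracy of the stated risk, which matters more because girls aged 15 to 17 would consent for themselves under a waiver justified by confidentiality. The other is that a co-member might repeat what she has learned to a girl's family or community. Clinic-based and community snowball recruitment makes it more plausible that members know one another.

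**Working it through.** **Inputs.** Four adolescent focus groups of 8, and one eligibility rule for all members (section 10(c)); inclusion of girls who have not disclosed to a caregiver (section 10(d)); risk text and safeguards (section 12(a)).

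**Reproducing the plan's figures.** 4 × 8 = 32 adolescents in focus groups, as stated. Over all components, 24 + 24 + 32 + 30 = 110 adolescents, which agrees with the lay summary.

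**Who learns what.** In a full group each girl has 8 − 1 = 7 co-members. Over four full groups there are 4 × 8 × 7 = 224 ordered pairs in which one girl comes to know that another has both conditions. This counts awareness inside the room. It is not a count of harms. The number of girls with an undisclosed condition in these groups cannot be derived, because section 10(d) sets no quota.

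**The condition needed.** The inference works for any member who knows the entry criteria. That is a reasonable assumption, since each member is recruited, screened and consented for a study of pregnant adolescents living with HIV.

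**Each stated measure against this route.**
- No personal questions: limits what is said, not what attendance implies.
- Private venue: protects against bystanders, not against members of the group.
- Individual sessions: given to in-depth interviews and the pilot only.
- Staff sensitivity, local knowledge and training, and care when entering homes: govern staff conduct, not what peers learn or repeat.
- Caregiver-knowledge rule: applies to dyadic interviews.
- Data security: protects records, not what members remember.
- Active referral of undisclosed girls: offers support, but does not restrict what the group learns.

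The supplied text contains no group confidentiality rule, no use of pseudonyms within the group, no check for acquaintances and no statement that attendance reveals status to co-members.

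**The case against.** The best reply has four parts.

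**The risk text is not blind to this route.** Just before its focus group sentence it names participation as a way in which status can come out. That stands, and it narrows the point: a route already recognised is not applied to co-members and is not carried into the safeguards.

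**Key documents are unseen.** The consent pages were removed before review, the monitoring plan is a separate attachment, and the focus group guide was not supplied. Section 12(a) says that consent explains risks and safeguards and that understanding is assessed. A warning or a ground rule could be in any of these. A reader might infer that no safeguard exists anywhere, or that girls would consent to an understated risk. The documents do not support either inference. What can be said is that the risk and safeguard text does not cover the route.

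**Peers are not caregivers.** Co-members share both conditions, and non-disclosure in section 10(d) means not having told a caregiver. The harm that the protocol describes needs a further step, in which a peer passes the information on. This also stands.

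**Acquaintance cannot be sized.** Section 5 describes a surveillance project in one Siaya sub-county: "Of these, 63 (5%) are HIV-infected; half (32/63) are single". A reader might set the 16 rural focus group members against those 32 and infer that half of the eligible girls would sit in two groups. The figures do not support this. The project is not the sampling frame. Each participant group is half rural and nobody joins more than one component, so 110 / 2 = 55 rural adolescents are needed, which already exceeds 32. The snowball flyers are the better evidence that members may know each other, and they give no percentage.

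None of this makes the focus group sentence complete or lets the listed safeguards reach co-members.

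**Conclusion.** The point holds in a limited form. For each girl in a full adolescent focus group, attendance makes both conditions known to 7 others, and this does not depend on her answers. The focus group sentence in section 12(a) presents disclosure as conditional on answering, and none of the listed safeguards limits what co-members learn or repeat.

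It is tempting to go further and call the named harm, including violence, certain. The documents do not support that. Awareness among co-members is close to certain given the eligibility rule. Onward disclosure to family or community, and any consequence of it, is only possible.

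The conclusion assumes full groups and members who know the entry criteria. It needs no estimate of the size of the eligible population. It does not question focus groups as a method and does not affect sample size or aims. Confidence is medium, because the unseen documents may already contain some of the measures below. The text should be corrected, and those documents checked, before girls consent to the groups.

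**What to change.** 1. Reword the risk text in section 12(a) to say that attending an adolescent focus group tells the other members that the girl is pregnant and living with HIV. Check that the focus group consent information says the same. While that sentence is open, reconcile its statement that pilot participants get no personal questions with section 10(e), which says they are asked about their own lives.
2. Add focus group safeguards to section 12(a): pseudonyms in the group; a confidentiality ground rule given at the start; and, where feasible, members drawn from different facilities, with acquaintances and girls linked by a snowball flyer placed in different groups.
3. As an option, let a girl who does not want to join a group after hearing this give the same feedback on the mock-ups one-to-one, using the existing individual-interview procedure. This should not be mandatory: the number of girls with an undisclosed condition is unknown, and moving all of them could shrink the groups.

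The cost is a few sentences of text and slightly harder scheduling. If the option is used, there is also some added staff time and some loss of group discussion.
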